#### 7.3.3 Safety analyses

The occurrence of dose limiting toxicity (DLT) as well as the incidence and intensity of adverse events graded according to CTCAE, laboratory parameters and vital signs will be evaluated.

Incidence and intensity of adverse events

The severity, and timing of adverse events will indicate how well the treatment regimen is tolerated. Toxicities will be evaluated using the CTCAE grading scheme. The overall incidence and intensity of adverse events, as well as relatedness of adverse events to treatment with BI 836826 will be reported for all treatment schedules. Serious adverse events will be tabulated. In addition, events leading to dose reduction or treatment discontinuation will be examined, but may not be reported as individual tables, depending upon the extent of overlap with the occurrence of DLT.

Descriptive statistics will be used to describe changes in laboratory tests over time. In addition, all abnormalities of potential clinical relevance will be reported. Events that started

Boehringer Ingelheim		
BI Trial No.: 1270.1		
c01568809-08	Trial Protocol	

within the period starting with first administration of the trial drug and ending six weeks after the last administration of BI 836826 will be considered as having occurred during treatment. In general, later events will be attributed to the post-study period and will be presented separately. However, post-study events will be examined to determine whether they need to be combined with on-treatment events in an additional table.

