## 4. **TREATMENTS**

## 4.1 TREATMENTS TO BE ADMINISTERED

In course 1, the total dose will be divided into two portions administered on day 1 and 2 (please refer to the Flow Chart: Course 1, Dosing on Day 1 and Day 2).

The dose on day 1 will be 10% of the total dose, but not exceed 10 mg in case the total dose is higher than 100 mg. The dose on day 2 will be the planned total dose minus the dose administered on day 1. If adverse events which are related to the infusion schedule, e.g. infusion-related reactions or tumour lysis syndrome require administration of a lower dose on day 2, the total dose in course 1 may be divided into 3 smaller portions on day 1, 2 and 8. In this case, the dose on day 1 will remain as defined previously. The difference between day 1 and the planned total dose level will be equally divided between day 2 and 8 (reference to appendix 10.6). The distribution of the planned total dose in course 1 to two, or if needed to three smaller portions will be based on safety data from the previous cohort and will be assessed and may be modified by the DSMB. If supported by the DSMB, the same rules may be applied to course 2 in case infusion-related adverse events can be controlled by the above measures in course 1 but occur in course 2.

In all subsequent treatment courses, BI 836826 will be administered as a rate-controlled intravenous infusion on day 1 of each 14-day course.

The first and second infusion will be started at a rate of 10 mL/h. The infusion rate should be increased every 30 (+/-10) minutes by 10 mL/h to a maximum of 80 mL/h as long as tolerated by the patient. If considered safe by the investigator, the stepwise increase of infusion rate during the third and subsequent infusions may be faster or steps may be omitted, but the maximum infusion rate must not exceed 120 mL/h. If symptoms of an infusion related reaction occur, the infusion should be temporarily stopped. Upon recovery, it should be resumed at 50% of the rate at which the reaction occurred for at least 30 minutes. Lower rates may be selected if clinically indicated. Depending on the time of occurrence and the severity of the reaction, the investigator may consider administering additional supportive medication, e.g. corticosteroids. A stepwise re-increase of the infusion rate to a maximum of 80 mL/h is possible.

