#### 6.2.2.3 Visit 2 - day 3 (day 3 in course 1 or day 3 (+2) in course 2-8)

On visit 2, the following parameters and investigations will be obtained/performed

- Vital signs (see Section 5.2.5.1)
- Adverse events
- Concomitant therapy
- Safety lab parameters as specified in Section 5.2.3.1
- 6.2.2.4 Visit 2 day 4 (day 4 only in course 1)
- Vital signs (see Section 5.2.5.1)
- Adverse events
- Concomitant therapy
- Safety lab parameters as specified in Section 5.2.3.1
- •

6.2.2.5 Visit 3 - day 8 (day 8 in course 1 and day 8 (+2) in course 2-8)

On visit 3, the following parameters and investigations will be obtained/performed

- Administration of BI 836826 only in course 1, if treatment schedule according to Section 10.6 is used
- Vital signs (see Section 5.2.5.1)
- Adverse events
- Concomitant therapy
- Safety lab parameters as specified in Section 5.2.3.1
- Blood samples to screen for evidence of tumour lysis syndrome only in course 1, if treatment schedule according to section 10.6 is used
- - CMV monitoring (see Section 5.2.3.3.2)
- 6.2.2.6 Visit 3 day 9 (day 9 only in course 1, if treatment schedule according to Section 10.6 is used)

On visit 3, the following parameters and investigations will be obtained/performed

- Vital signs (see Section 5.2.5.1)
- Adverse events
- Concomitant therapy
- Safety lab parameters as specified in Section 5.2.3.1
- Blood samples to screen for evidence of tumour lysis syndrome
- •

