Change 8: "BI 836826 will be administered as an intravenous infusion over a period of 3 hours on day 1 of each 14-day course. In case a patient experiences an adverse event during the infusion" was replaced by "In course 1, the total dose will be divided into two portions administered on day 1 and 2 (please refer to the Flow Chart: Course 1, Dosing on Day 1 and Day 2). The dose on day 1 will be 10% of the total dose, but not exceed 10 mg in case the total dose is higher than 100 mg. The dose on day 2 will be the planned total dose minus the dose administered on day 1. If adverse events which are related to the infusion schedule, e.g. infusion-related reactions or tumour lysis syndrome require administration of a lower dose on day 2, the total dose in course 1 may be divided into 3 smaller portions on day 1, 2 and 8. In this case, the dose on day 1 will remain as defined previously. The difference between day 1 and the planned total dose level will be equally divided between day 2 and 8 (reference to section 10.6). The distribution of the planned total dose in course 1 to two, or if needed to three smaller portions will be based on safety data from the previous cohort and will be assessed and may be modified by the DSMB. If supported by the

[	DSMP the same miles may be applied to entry
	DSMB, the same rules may be applied to course 2 in case infusion-related adverse events can be controlled by the above measures in course 1 but occur in course 2.
	In all subsequent treatment courses, BI 836826 will be administered as a rate-controlled intravenous infusion on day 1 of each 14-day course.

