"If no signs of progression please continue to Visit 1 Flow Chart Course 2-8. If the patient has disease progression or withdraws, please continue to EOT." was added
"The time for infusion may vary, depending on infusion rate and occurrence of infusion-related reactions. The exact start and end time of the infusion should be recorded. The assumed planned time of 5 hours is based on a stepwise increase of the rate every 30 (+/-10) minutes by 10 mL/h to a maximum of 80 mL/h without any interruptions." was added
"If the time for infusion prolongs is longer than 3 hours, e.g. in case of infusion related reactions, the exact start and end time should be recorded. If the infusion is interrupted, the stop time and the time when it is re-started need to be documented " was deleted
Change 25:The whole section 10.5 was added Change 26:The whole section 10.6 was added

Rationale for change	Changes 1, 2, 8, 9, 10, 24, 26: To prevent infusion related reactions or tumour lysis syndrome after the first infusion, the infusion schedule for course 1 will be modified. Modification will include two elements: a small dose on day 1 to lower the risk
	for reactions related to the first infusion and to improve tolerability of a larger dose on day 2, and a slower infusion rate.
	The total dose in course 1 will be divided into 2 smaller portions. The dose on day 1 will be reduced to 10% of the planned dose and will not exceed 10 mg at planned doses of 100 mg and

Page 98 of 111

above. The planned dose minus the dose
administered on day 1 will be given on day 2. In case infusion related adverse events on day 2
would require also a modification of the infusion
on day 2, the dose in course 1 may be distributed
to days 1, 2 and 8 in agreement with the DSMB.
Due to the change in the infusion scheme the
Flow Chart was split in course 1 and course 2-8 (change 2), and a separate Flow Chart for the
distribution of the total dose to 3 portions was
provided (change 25). The infusion will remain
rate controlled, but the infusion rate will be
increased in small steps as tolerated by the patient not only in course 1 but in all treatment
courses. Therefore the time for infusion will be
longer than 3 hours and time for infusion will
vary.
Change 3: Clarification and update of Table of
Contents
Change 4: Explanation of abbreviation
Change 5: Clarification of definition of sequential enrolment
enroimeni
Changes 6 and 11: Intra-patient dose escalation

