6. GENERAL ANALYSIS DEFINITIONS

6.1 TREATMENTS

In this Phase I trial, treatments are not randomised (open-label, dose escalation). Different dose levels of BI 836826 are being administered. The data will be presented for all dose cohorts separately and in total over all dose cohorts. To justify the MTD determination, DLTs occurring during the MTD evaluation period (during the first treatment course) will be presented separately from those occurring during the complete on-treatment period.

"Analysing treatment" will be used for reporting of treatment emergent adverse events (AE) and to differentiate between screening, on-treatment, post-treatment and post-study safety data. The inequalities start date \leq onset date of AE < end date will determine whether the AE will be assigned to the "analysing treatment" or not. Table 6.1:1 defines the "analysing treatment period" which will be used for reporting of treatment emergent AEs and safety laboratory parameters. Safety data recorded during the Residual Effect Period (REP) will be considered as on-treatment.

If not specified otherwise, all safety tables will be based on the on-treatment period. AEs that have an onset date during the screening or post-study periods will be displayed in separate listings from those occurred during the on-treatment period.

T 11 (1	1 D C '.'	C 1 .		. 1()
Table 6 1:	I Definition	of analysing	treatment	neriodist
I dolo o.i.	1 Dominion	OI unui yonii 🗲	, u cuuniciit	periodisi

Analysing treatment period	Start date (including)	Stop date (excluding)	
Screening	Date of informed consent	Date of first administration of study medication	
On-treatment	Date of first administration of study medication	Start date of 'Follow-up'	
Follow-up	Date of end of REP +1	Start date of 'Post-study'	
Post-study	Last date patient status obtained / last date patient known to be alive + 1 (if patient is lost to follow-up) / date of refusal + 1 day / the date patient died + 1	During the trial: open / empty; after database lock (DBL): DBL + 1 day	

The initial study medication assigned at the beginning of the first treatment course will be used as the label of the analysing treatment.

The actual dose of study medication administered on the day each AE started will also be derived. This will be presented in patient listings, but will not be used for defining treatments for analysis.

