7.8.1.2 Adverse events

Unless otherwise specified, adverse events analysis will be performed for on-treatment periods. Selected analyses (e.g. summary of AEs) will be repeated for the MTD evaluation period.

The analyses of AEs will be descriptive in nature and will follow the standard procedure laid down in the DM & SM (including all required tables and listings; guideline _'Handling and Summarization of AE Data for CTR and Integrated Summaries' (4). AEs will be coded with the most recent version of Medical Dictionary for Regulatory Activities (MedDRA). The version number will be displayed as a footnote in the respective tables and listings.

The system organ classes will be sorted alphabetically. In tables displaying AEs by dose cohort preferred terms will be sorted by descending frequency of adverse events in the "Total" BI 836826 group.

Each patient can be observed during the trial under several doses. Analysing the AE of all treatment courses will be carried out under the initial treatment. No formal statistical analysis is planned for the safety comparison.

The analysis of AEs will be based on the concept of treatment emergent AEs. That means that all adverse events occurring between first administration of BI 836826 until 6 weeks after last administration of BI 836826 will be assigned to the on-treatment period. All adverse events occurring before first administration of BI 836826 will be assigned to "Screening" and all adverse events occurring after last administration of BI 836826 + 6 weeks will be assigned to "post-study (for listings only). The actual planned dosage of BI 836826 administered on the day each AE starts will also be derived and will be included in the listing. Listings of screening events will not be sorted by initial treatment. Post-study listings will be sorted by initial treatment. For details on the treatment definition please refer to Section 6.1.

According to the BI standards, multiple recordings of AEs will be collapsed to episodes on the lowest level term and multiple episodes will be condensed to records on the PT and system organ class (SOC) level. CTCAE grade will be an additional criterion for collapsing and condensing AEs. The maximum CTCAE grade will be assigned to episodes and records. CTCAE grade and DLT information will be displayed in AE listings. MedDRA levels for condensing will be SOC and PT.

An overall summary of adverse events will be presented.

Reporting of CTCAE grades

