7.8.1.3 Protocol-specified significant adverse events

Protocol-specified significant AEs are defined in the CTP, Section 5.2.2.1.

Infusion-related reactions (IRR)

Frequency of IRRs with CTCAE grade 3 or higher will be displayed in separate listings and tables where it will be differentiated between the reported AE term "Infusion-related reaction" and the symptoms of an IRR that are reported as AEs.

For patients at the beginning of this trial (up to the 9 mg dose cohort), the term IRR only or the symptoms of an IRR reported as AEs but not captured explicitly as symptoms of an IRR. For these patients, potential symptoms of an IRR can be only identified over pre-defined AE preferred terms (refer to Table 9.4:1).

For patients from following dose cohorts (including some patients of the 9 mg cohort), not only IRRs are reported with the AE term "Infusion-related reaction" but also their symptoms which are additionally marked as symptoms of an IRR.

A listing will show all patients with IRR episodes as well as reported symptoms of these IRRs. Furthermore symptoms of IRRs will also be displayed where it will be distinguished between symptoms marked as such and potential symptoms of an IRR (up to the 9mg dose cohort only).

The number of episodes of IRRs as well as the frequency of its symptoms and CTCAE grades will be displayed graphically for those patients where the symptoms of an IRR are reported as such.

The frequency of the AE "Infusion-related reaction" episodes will be displayed graphically by administration visit together with its CTCAE grade for all patients.

Tumour lysis syndrome

A frequency table displaying patients with clinical TLS (TLS reported as protocol-specified significant AE) will be provided. Additionally to cases of clinical TLS, laboratory TLS will be analysed (please refer to Section 7.8.2).

Any event that qualifies for DLT

Please refer to Section 5.2.1.1 of the CTP.

Drug-induced liver injury (DILI)

Please refer to Section 5.4.4. The frequencies of these protocol-specified significant AEs will be displayed in the CTR.

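### The SAP shows adverse events and infusion reactions by dose cohort and in total but never by course 1 infusion schedule, so trends in infusion reactions or tumour lysis may reflect schedule as well as dose

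*Protocol*

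**What the plan says.** **Protocol.** Section 7.3.3 states that the incidence and intensity of adverse events, "as well as relatedness of adverse events to treatment with BI 836826 will be reported for all treatment schedules". The term *treatment schedule* is not defined. Section 6.2.2.5 uses it for the way course 1 is divided: "Administration of BI 836826 only in course 1, if treatment schedule according to" Section 10.6.

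Section 4.1 divides the course 1 dose between days 1 and 2: "The dose on day 1 will be 10% of the total dose, but not exceed 10 mg" once the total exceeds 100 mg, with the remainder on day 2. If events related to the infusion schedule require it, the remainder is halved between days 2 and 8. IRRs and tumour lysis syndrome (TLS) are its own examples of such events. The choice rests on safety data from the previous cohort, may be altered by the DSMB, and may be extended to course 2.

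The modification log is used here only as history. It shows that course 1 was previously an "intravenous infusion over a period of 3 hours on day 1 of each 14-day course". Modification 3 (2 August 2012) gives the reason for the change: "To prevent infusion related reactions or tumour lysis syndrome after the first infusion, the infusion schedule for course 1 will be modified". The same rationale names two elements, a small first dose and a slower infusion rate.

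**SAP.** Section 6.1: "The data will be presented for all dose cohorts separately and in total over all dose cohorts". Section 7.8.1.2: "Analysing the AE of all treatment courses will be carried out under the initial treatment". The actual dose on the day an event starts is listed but is not used for grouping (6.1). In 7.8.1.3, IRR "episodes will be displayed graphically by administration visit together with its CTCAE grade for all patients". No readable table or figure is broken down by course 1 schedule.

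**The concern.** By the protocol's own account, IRRs and TLS depend on how the first course is infused. Patients enter in order of rising dose (Protocol 7.1), so anything that changes with calendar time also tends to change with dose. A dose-cohort table that does not say how each cohort was infused leaves the reader unable to tell a dose effect from a schedule effect. IRRs could appear to fall as dose rises, or a real rise could be hidden.

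The all-patient figure has a further difficulty. Its course 1 day 1 position can hold the full course dose for one patient and a tenth of it for another. At stake is the interpretation of the infusion-reaction and tumour-lysis profile carried into later trials. The DLT count that fixes the MTD is not affected.

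**Working it through.** **The plan's own figures.** The planned cohort sizes (Protocol 7.6) reproduce: 3×1 + 3×3 + 3×6 = 30 in escalation, and 30 + 30 = 60 with the expansion cohort. They matter here only because they show how small the cells are: 1, 3 or 6 patients per escalation cohort. No test, alpha or power is planned (Protocol 7.2).

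**First-infusion dose.** For a nominal course dose D, a single infusion gives D on day 1. The current rule gives min(0.1 × D, 10 mg) on day 1. Day 2 is then D minus the day 1 portion, or half of that difference if day 8 is also used.

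| D (mg) | Day 1, single | Day 1, split | Ratio | Day 2, two portions | Day 2, three portions |
|---|---|---|---|---|---|
| 1 | 1 | 0.1 | 10 | 0.9 | 0.45 |
| 9 | 9 | 0.9 | 10 | 8.1 | 4.05 |
| 25 | 25 | 2.5 | 10 | 22.5 | 11.25 |
| 50 | 50 | 5 | 10 | 45 | 22.5 |
| 100 | 100 | 10 | 10 | 90 | 45 |
| 200 | 200 | 10 | 20 | 190 | 95 |

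The ratio is 10 up to 100 mg and grows above that because of the 10 mg cap. A split 9 mg patient starts at 0.9 mg, below an unsplit 1 mg patient. Between the two current schedules the day 1 dose is identical and the day 2 dose differs by a factor of 2 (for example 8.1 / 4.05). The 10-fold gap therefore arises only if some patients had the single infusion. The documents do not say which cohorts, if any, did.

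**What pooling can do (illustration, rates assumed).** Let p1 be the first-infusion IRR risk on a single infusion, p2 the risk on the split schedule, and k the number of single-infusion patients among 6 who are pooled. The displayed rate is (k × p1 + (6 − k) × p2) / 6.

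- p1 = 60%, p2 = 30%: 30% at k = 0, 45% at k = 3, 60% at k = 6.
- p1 = 80%, p2 = 40%: 40% at k = 0, 60% at k = 3, 80% at k = 6.
- p1 = p2 = 50%: 50% at every k, so no distortion.

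If instead the schedule changed between cohorts, the first pair of rates would show 60% in the lower cohorts and 30% in the higher ones with no dose effect at all. None of these rates is in the documents.

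**TLS.** Ascertainment also varies by schedule. Protocol 5.2.3.2 adds 24 hours of TLS monitoring after a day 8 infusion, which only three-portion patients receive.

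**The case against.** A reader might infer that the SAP breaks a protocol commitment. The documents do not support that. Reporting *for* all schedules is not reporting *by* schedule, and tables covering every treated patient satisfy the sentence literally. None of the five modification logs lists 7.3.3 as changed, so the phrase appears to predate split dosing. The log also shows that the schedule wording in 6.2.2.5 was itself added by modification 3, so it cannot settle what 7.3.3 meant. SAP 4.1 therefore had nothing it was bound to declare.

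A reader might also infer that individual cohorts mix schedules. This is not shown. Section 4.1 ties the split to the previous cohort's data, which suggests decisions cohort by cohort. The break inside the 9 mg cohort in SAP 7.8.1.3 concerns how IRR symptoms were captured, not how the drug was infused. The day 8 portion is only an option.

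Nor would tabulating by schedule show whether splitting the dose worked. Dose division and infusion rate changed together, and a change at a cohort boundary leaves dose and schedule aliased however the table is laid out.

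The SAP does offer more than cohort tables: IRR and symptom listings, a listing of every administration (7.3), a listing of each dose at each course (7.7), and selected adverse event summaries repeated for the MTD evaluation period. Comparing schedules is not a trial objective, and IRRs are excluded from the DLT definition.

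All of this stands, and it limits the point to a modest one. It does not remove it. Listings leave the reader to rebuild each patient's schedule by hand, and the all-patient figure and the total column still pool whatever schedules were used.

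**Conclusion.** This is a worthwhile, low-cost improvement to the displays, not a departure from the protocol. It rests on one condition that the documents leave open: that patients were treated under more than one course 1 schedule. If so, the total column and the all-patient IRR figure combine unlike infusions. Where single-infusion patients are included, first-infusion doses differ 10-fold for the same nominal dose up to 100 mg. Trends in IRRs or TLS across cohorts may then reflect schedule, including infusion rate, as well as dose.

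The size of any distortion cannot be calculated from the documents, and it could be nil. The ADS Plan that holds the treatment labels (SAP 6.1) was not available and parts of the SAP are blacked out, so a schedule label may exist that cannot be seen here.

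**What to change.** In SAP 7.8.1.2 and 7.8.1.3:

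1. Derive each patient's actual course 1 schedule (day 1 only; days 1+2; days 1+2+8) from the administration data.
2. Footnote each dose cohort with the number of patients on each schedule.
3. Split by schedule the IRR figure by administration visit, and the total column for IRRs and TLS in course 1. Show the dose given at each infusion.
4. Subdivide within a dose cohort only where it contains more than one schedule.
5. State that where the schedule changed at a cohort boundary, dose and schedule, including infusion rate, cannot be separated.

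The cost is some SAP wording and a few extra displays from data already due to be listed under 7.3 and 7.7. The drawback is small cells, which is why item 4 is limited. No dosing rule, DLT count or MTD determination changes.
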